6.1.3.1 Handling of missing values/censoring/discontinuations

Missing values will be assumed missing at random. No imputation of missing values will be done for any analyses.

6.1.3.2 Graphical presentation of results

Boxplots to visualize treatment differences in stool frequency and stool form will be created.

6.1.3.3 Supportive analysis

Baseline weekly stool frequency and the corresponding average stool form will be analyzed using the same method as described in Section 6.1.3 to assess unequal carryover effects.

The number and percentage of subjects using loperamide will be tabulated by treatment. Total weekly loperamide use (in mg) will be summarized by treatment and visit (including baseline). The stool index, calculated as [weekly stool frequency*mean stool form]+loperamide use [weekly mg*3], will also be summarized and analyzed using a linear mixed effects model including sequence, period and treatment as fixed effects and subject nested within sequence as a random effect.

Corporate Confidential Information

7 Statistical methods for safety and tolerability data

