2.2 Secondary objective(s)

Secondary objective(s)	Endpoints related to secondary objective(s)

• To assess the pharmacokinetics of LJN452 in pBAD patients.• To assess the effect of LJN452 on use of rescue medications during the study period.	
• Tmax, Cmax and AUCtau of LJN452.• Use and type of rescue medications.

Corporate Confidential Information

3 Investigational plan

[figure not shown]

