3.2 Rationale of study design

This randomized, multi-center, double blind (patient and investigator blind, sponsor open label), placebo-controlled, cross-over study is designed to assess safety, tolerability and efficacy of LJN452 at 60 μ g relative to placebo in patients with pBAD, as assessed by a reduction in stool frequency and stool type score after 2 weeks of double-blind treatment.

A cross-over design reduces variability as the treatment comparison can be done within patient.

Randomization will be maintained at 1:1 ratio over the entire study in order to avoid any sequence bias.

Multiple sites will be used to enroll patient in this study due to the underlying prevalence of diagnosed pBAD. It is known that differences in criteria exist in the diagnosis of pBAD in different regions.

In order to maintain the scientific integrity of the study, investigators and patients will remain blinded regarding the allocation of active or placebo. The clinical trial team will be unblinded throughout the dosing phase to allow analysis of safety and PK/PD data.

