11.3 Treatments (study drug, rescue medication, other concomitant therapies, compliance)

Data for study drug administration (rescue medication) and concomitant therapies will be listed by treatment sequence and patient.

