11.5 Analysis of secondary and exploratory variables

The number and percentage of subjects using loperamide will be tabulated by treatment. Total weekly loperamide use (in mg) will be summarized by treatment and visit (including baseline). The stool index, calculated as [weekly stool frequency*mean stool form]+loperamide use [weekly mg*3], will also be summarized and analyzed using a linear mixed effects model including sequence, period and treatment as fixed effects and subject nested within sequence as a random effect.

Corporate Confidential Information

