6.1.2 Descriptive analyses

Summary statistics (including median and IQR) of the stool frequency and average stool form (weekly and biweekly) for each treatment as well as the difference and % change between the 2 treatments will be provided by visit. Baseline data will be summarized by treatment and visit. The number and percentage of patients with each stool form will be provided by treatment and visit. The stool frequency and stool form data will be listed by treatment sequence, patient and visit.

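### In the visible text, the rescue-medication objective is addressed only descriptively: loperamide use has no planned within-patient drug-placebo estimate or confidence interval

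*SAP*

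**What the plan says.** Protocol 2.2 words the objective as an effect: "To assess the effect of LJN452 on use of rescue medications during the study period". SAP 1.3.2 repeats it. The matching endpoint is "Use and type of rescue medications", which names no contrast.

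For loperamide itself, three things are planned in the visible text:

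- **Any use.** SAP 6.1.3.3 states: "The number and percentage of subjects using loperamide will be tabulated by treatment". Protocol 11.5 has the same sentence.
- **Amount.** Both sections summarise total weekly milligrams for each treatment at each visit, baseline included.
- **Listing.** Protocol 11.3 states: "Data for study drug administration (rescue medication) and concomitant therapies will be listed by treatment sequence and patient".

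The only visible model that contains loperamide is for a composite: "The stool index, calculated as [weekly stool frequency*mean stool form]+loperamide use [weekly mg*3], will also be summarized and analyzed using a linear mixed effects model". It has fixed terms for sequence, period and treatment and a random subject effect within sequence.

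Other variables get more. For the stool variables, SAP 6.1.2 plans summaries for each treatment "as well as the difference and % change between the 2 treatments will be provided by visit", and SAP 6.1.3 adds a repeated measures model with 95% simultaneous regions. SAP 7.1.2 applies a crossover mixed model to lipids and liver tests. Protocol 3.2 gives the reason for the design: "A cross-over design reduces variability as the treatment comparison can be done within patient".

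**The concern.** An objective worded as an effect needs a contrast between drug and placebo and a statement of how precise it is. The planned tables give one column per treatment. They do not report the pairing of the two periods within a patient, they are not adjusted for period, and they carry no interval. As written, the trial can describe rescue use under each treatment but cannot state the effect with any precision, although the design was chosen to allow that comparison.

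The gap also touches the primary result. Exclusion criterion 4 exempts loperamide from a bar on agents that alter GI transit, and the drug is allowed throughout treatment. A difference in stool frequency or form is hard to read without an estimate of the difference in rescue use.

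**Working it through.** The documents give no loperamide rate, standard deviation or within-patient correlation, and the sample size section is redacted, so there is no plan figure to reproduce. The only planning input used is 24 completers (protocol 3.1, SAP 1.4). All other inputs below are assumptions for illustration.

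**1. Any use: does the planned table determine the precision?** Assume 16 of 24 patients use loperamide on placebo and 10 of 24 on drug. The reduction (placebo minus drug) is 6/24 = 25 points. Let b be the patients who use it on placebo only and c those who use it on drug only. Then b - c = 6, users in both periods number 10 - c, and users in neither number 8 - c, so c can run from 0 to 8. The paired Wald interval uses SE = sqrt[(b + c) - (b - c)²/n] / n.

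- First case, 6 v 0: SE = sqrt(6 - 36/24)/24 = 0.0884, and 0.25 ± 1.96 × 0.0884 gives 0.077 to 0.423.
- Last case, 14 v 8: SE = sqrt(22 - 36/24)/24 = 0.1887, and 0.25 ± 1.96 × 0.1887 gives -0.120 to 0.620.

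| b | c | Both periods | Neither | Paired 95% interval | Exact McNemar p |
|---|---|---|---|---|---|
| 6 | 0 | 10 | 8 | 8% to 42% | 0.03 |
| 10 | 4 | 6 | 4 | -4% to 54% | 0.18 |
| 14 | 8 | 2 | 0 | -12% to 62% | 0.29 |

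The planned table is identical in every row.

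**2. Does the stool index stand in for rescue use?** The index is frequency × form + 3 × mg. A fall of 28 mg per week moves it by 3 × 28 = 84 points. A fall of 14 stools per week at an assumed form of 6 also moves it by 14 × 6 = 84 points. If rescue use rises by the first amount while stools fall by the second, the index does not change. A treatment effect on the index therefore cannot be attributed to rescue use.

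**3. What would an estimate of weekly milligrams deliver?** With one value per patient and period, 24 completers and 22 degrees of freedom, the 95% half-width is t × sqrt[2(1 - rho)/24] standard deviations, with t = 2.074. At assumed within-patient correlations of 0.3, 0.5, 0.7 and 0.8 this gives 0.50, 0.42, 0.33 and 0.27 standard deviations.

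**The case against.** The strongest objection is redaction. The protocol's contents list names a section 11.5.1 on efficacy and pharmacodynamics, and where it should appear there is a redacted block. Another block follows SAP 6.1.3.3. An analysis of rescue use could sit in either. This stands as a caveat, and the point is limited to the visible text. It does not remove the point, because the loperamide paragraph is unredacted, reads as complete and is the same in both documents. In both documents the secondary objectives are also printed in full with a redacted block after them, which suggests that the hidden material is exploratory.

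It is also fair to say that description is a defensible choice here. The trial is non-confirmatory, protocol 11.7 says that power for secondary objectives was not assessed, and the endpoint names no contrast. That excuses the lack of a test or a power statement. It is a weaker excuse for having no estimate and interval in a study meant to guide further development. With complete data and equal sequence sizes, subtracting the treatment means does give the within-patient mean difference, but not its precision. If 30 are enrolled and 24 complete, up to 30 - 24 = 6 patients may contribute one period only, and the two columns then compare partly different patients.

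Two stronger readings are tempting and are not supported. A reader might infer that the index effect is mostly a frequency and form effect because loperamide is a minor share of the index. Share of level says nothing about share of effect: if weekly use fell from 28 to 6 mg with stools unchanged, the index would fall by 3 × 22 = 66 points, all from loperamide. A reader might also take the gain from a paired over an unpaired standard error as precision lost under this plan. The plan makes no unpaired inference on loperamide, so there is no such loss to measure.

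**Conclusion.** The point holds in limited form. In the visible text, loperamide use is tabulated, summarised and listed, but neither measure has a planned within-patient estimate or interval, and the modelled index does not isolate it. The consequence is that one of two secondary objectives would be reported without stated precision. In the illustration, one and the same table is compatible with an interval that excludes zero and with one that runs from -12% to 62%. Those figures rest on assumed counts and a Wald interval, and show only that the margins are insufficient. They do not predict this trial's result.

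The weight is modest. No figure in the documents is contradicted, the data are already collected in the diary, and the gap can be closed cheaply before database lock. If a redacted section already holds such an analysis, only a cross-reference is needed.

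**What to change.** In SAP 6.1.3.3 and protocol 11.5, label the following as the analysis of the rescue-medication objective:

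- **Lead analysis.** The drug-minus-placebo difference in weekly loperamide milligrams with a 95% confidence interval, from the mixed model already specified for the stool index. State that each patient contributes one value per period (the mean of the two weekly totals), so that the single random subject effect is adequate.
- **Sensitivity analysis for skew and zeros.** A Hodges-Lehmann estimate and interval comparing within-patient period differences between the two sequences. Halve it, because that shift is twice the treatment effect.
- **Any use.** Add to the planned table the counts of discordant pairs and the paired risk difference with a 95% interval. Name the interval method in advance, since the Wald form is unreliable with few discordant pairs.

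Keep the existing summaries, and present the new results as non-confirmatory estimates. The cost is a few lines of text, about one extra table and a little programming, with no new data. The drawback is that intervals may be wide with about 24 completers, and the report should say so.

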7.1 Primary objective

To determine the safety and tolerability of LJN452 in patients with pBAD.

7.1.1 Variables

Adverse events, vital signs (blood pressure, pulse rate, body temperature), ECG intervals, laboratory measurements, as well as patient demographics, baseline characteristics, and treatment information.

7.1.2 Descriptive analyses

Patient demographics and other baseline characteristics

All data for background and demographic variables will be listed by treatment sequence and patient. Summary statistics will be provided for all patients, as well as for each treatment sequence.

Relevant medical history, current medical conditions, results of laboratory screens, drug tests and any other relevant information will be listed by treatment sequence and patient.

Treatment

Data for study drug administration and concomitant therapies will be listed by treatment sequence and patient.

Vital signs

All vital signs data will be listed by treatment sequence, patient, and visit/time and if ranges are available abnormalities (and relevant orthostatic changes) will be flagged. Summary statistics will be provided by treatment and visit/time.

ECG evaluations

All ECG data will be listed by treatment sequence, patient and visit/time, abnormalities will be flagged. Summary statistics will be provided by treatment and visit/time.

Clinical laboratory evaluations

All laboratory data will be listed by treatment sequence, patient, and visit/time and if normal ranges are available abnormalities will be flagged. A separate listing is provided presenting all parameters in a patient with any abnormal values. Summary statistics will be provided by treatment and visit/time. Baselines will be the last available measurement in each treatment period post washout and prior to dosing.

Log-transformed lipid (total Cholesterol, LDL, HDL, triglycerides) and LFT (GGT, ALP, AST, ALT) data will be analyzed using a mixed effects model including sequence, period, and treatment as fixed effects and subject nested within sequence as a random effect.

Adverse events

All information obtained on adverse events will be displayed by treatment and patient.

The number and percentage of patients with adverse events will be tabulated by body system and preferred term with a breakdown by treatment. An adverse event starting in one period and continuing into the next period is counted only in the onset period. A patient with multiple adverse events within a body system and treatment period is only counted once towards the total of this body system and treatment.

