- no action taken (i.e. further observation only)
- study treatment dosage adjusted/temporarily interrupted
- study treatment permanently discontinued due to this adverse event
- concomitant medication given
- non-drug therapy given
- patient hospitalized/patient's hospitalization prolonged

6. its outcome (not recovered/not resolved; recovered/resolved; recovering/resolving, recovered/resolved with sequelae; fatal; or unknown)

Once an adverse event is detected, it should be followed until its resolution or until it is judged to be permanent, and assessment should be made at each visit (or more frequently, if necessary) of any changes in severity, the suspected relationship to the study drug, the interventions required to treat it, and the outcome.

Information about common side effects already known about the investigational drug can be found in the Investigator Brochure (IB) or Core Data Sheet (for marketed drugs) or will be communicated between IB updates in the form of Investigator Notifications. This information will be included in the patient informed consent and should be discussed with the patient during the study as needed.

The investigator should also instruct each patient to report any new adverse event (beyond the protocol observation period) that the patient, or the patient's personal physician, believes might reasonably be related to study treatment. This information should be recorded in the investigator's source documents; however, if the AE meets the criteria of an SAE, it must be reported to Novartis.

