9.2 Serious adverse event reporting

9.2.1 Definition of SAE

An SAE is defined as any adverse event (appearance of (or worsening of any pre-existing) undesirable sign(s), symptom(s) or medical conditions(s) which meets any one of the following criteria:

- is fatal or life-threatening
- results in persistent or significant disability/incapacity
- constitutes a congenital anomaly/birth defect
- requires inpatient hospitalization or prolongation of existing hospitalization, unless hospitalization is for:
 - routine treatment or monitoring of the studied indication, not associated with any deterioration in bile acid malabsorption diarrhea
 - elective or pre-planned treatment for a pre-existing condition that is unrelated to the indication under study and has not worsened since the start of study drug

- treatment on an emergency outpatient basis for an event not fulfilling any of the definitions of a SAE given above and not resulting in hospital admission
- social reasons and respite care in the absence of any deterioration in the patient's general condition
- is medically significant, i.e. defined as an event that jeopardizes the patient or may require medical or surgical intervention.

Life-threatening in the context of a SAE refers to a reaction in which the patient was at risk of death at the time of the reaction; it does not refer to a reaction that hypothetically might have caused death if more severe.

All malignant neoplasms will be assessed as serious under "medically significant" if other seriousness criteria are not met.

Any suspected transmission via a medicinal product of an infectious agent is also considered a serious adverse reaction.

Medical and scientific judgment should be exercised in deciding whether other situations should be considered serious reactions, such as important medical events that might not be immediately life threatening or result in death or hospitalization but might jeopardize the patient or might require intervention to prevent one of the other outcomes listed above. Examples of such events are intensive treatment in an emergency room or at home for allergic bronchospasm, blood dyscrasias or convulsions that do not result in hospitalization or development of dependency or abuse.

All AEs (serious and non-serious) are captured on the CRF, SAEs also require individual reporting to DS&E as per [Section 9.2.2](#).

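### A continuing adverse event is counted only in its onset period, with no exception for worsening, so a rise in grade after crossover is missing from the later treatment's column

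*SAP*

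**What the plan says.** Safety and tolerability is one of the two primary objectives; SAP 7.1 words it as "To determine the safety and tolerability of LJN452 in patients with pBAD". Protocol 2.1 lists the type and frequency of adverse events among the endpoints for it.

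SAP 7.1.2 describes the summary table: "The number and percentage of patients with adverse events will be tabulated by body system and preferred term with a breakdown by treatment". Two counting rules apply. A patient with several events in one body system and treatment period counts once toward that body system and treatment. The rule at issue here is: "An adverse event starting in one period and continuing into the next period is counted only in the onset period". Protocol 11.5.2 contains both rules. Neither section mentions an increase in grade, a change to serious, or a treatment-emergent definition.

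On follow-up, Protocol 9.1 says that once an event has been detected, "assessment should be made at each visit (or more frequently, if necessary) of any changes in severity". The items to be recorded there include a CTCAE grade, start and end dates, seriousness and outcome. A date of grade change is not among them.

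SAP 7.1.2 also says: "All information obtained on adverse events will be displayed by treatment and patient".

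**The concern.** In a crossover, a by-treatment table should show what happened under each treatment. Suppose a mild event begins on placebo, lasts through washout, and becomes severe after LJN452 is started. Under the rule this patient adds one to the placebo column and nothing to the drug column. The worsening occurred on drug, but the table of adverse event frequency, which serves a primary objective, shows it nowhere under drug.

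The laboratory summaries are treated differently. SAP 7.1.2 takes a baseline in each treatment period, after washout and before dosing, so a laboratory value that worsens on drug is attributed to drug. Adverse events have no equivalent. The table as described also has no severity breakdown that would reveal a change in grade.

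At stake is the accuracy of a descriptive percentage in a small trial whose purpose (Protocol 1.2) is to guide further development. No hypothesis test depends on it.

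**Working it through.** The documents state no adverse event rate, so there is no plan figure to reproduce. The check has two parts: how the text handles worsening, and how much each affected patient matters.

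**Reading the text**

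1. The counting rule turns on the onset period alone (SAP 7.1.2, Protocol 11.5.2).
2. Protocol 9.1 follows changes in severity within an event already detected. It gives no instruction to open a new record when the grade rises.
3. Worsening of a pre-existing sign or symptom is mentioned in the serious adverse event definition (Protocol 9.2.1), but the counting rule does not refer to it.
4. Taken together, one event has one onset date and is counted once, under the treatment of that period, whatever its later grade.

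**Inputs**

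- N = 30 enrolled, 24 completers (SAP 1.4).
- Sequences allocated 1:1 (Protocol 6.2), so 30/2 = 15 placebo-first patients, or 24/2 = 12 among completers.
- Washout of 7 to 28 days (SAP 1.4).
- Assumed: p, the risk of an adverse event on placebo, 0.10 to 0.40.
- Assumed: s, the share of those events that last through washout and worsen on drug, 0.05 to 0.25.

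**Effect per patient**

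If k placebo-first patients are affected, the drug column is too low by k/N. For k = 1 this is 1/30 = 3.3 points, or 1/24 = 4.2 points. The placebo column does not change for these patients, because the onset is correctly counted there.

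**Expected number affected**

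Expected patients = (N/2) × p × s. Chance of at least one = 1 − (1 − p × s)^(N/2).

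| N | p | s | Expected patients | Points off drug column | Chance of at least one |
|---|---|---|---|---|---|
| 30 | 0.10 | 0.05 | 15 × 0.005 = 0.075 | 0.25 | 7% |
| 30 | 0.20 | 0.10 | 15 × 0.02 = 0.30 | 1.0 | 26% |
| 30 | 0.40 | 0.25 | 15 × 0.10 = 1.5 | 5.0 | 79% |
| 24 | 0.10 | 0.05 | 12 × 0.005 = 0.06 | 0.25 | 6% |
| 24 | 0.20 | 0.10 | 12 × 0.02 = 0.24 | 1.0 | 21% |
| 24 | 0.40 | 0.25 | 12 × 0.10 = 1.2 | 5.0 | 72% |

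These figures ignore one further condition, so they lean high. A row loses the patient only if that patient has no other drug-period event in the same row. A second event in the same body system would keep the body-system total right, although the preferred-term row could still miss the patient.

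**The case against.** The strongest reply is that the rule speaks of an event continuing, not worsening, and that the documents never say outright whether a rise in grade is a new event. If sites opened a new record with its own onset date, the worsening would count under drug. This is possible, but Protocol 9.1 points the other way, to one event followed over time. If site practice did vary, that too would call for a written rule.

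Several other points stand and limit the concern:

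- The rule is symmetric. A drug-onset event that worsens on placebo is likewise left out of the placebo column. For events that continue unchanged, onset-only counting is sensible, because it stops persisting drug events from inflating placebo.
- The event is not lost. It remains in the display of all adverse event information. The grade-based criteria in Protocol 7.1 and 7.4 do not use the onset-period count.
- The trial is non-confirmatory, the table is descriptive, and laboratory changes are summarized by treatment separately.

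A reader might infer that the rule could erase or reverse a sizable excess of events on drug. The documents do not support that. A 10-point shift at N = 30 needs three affected patients, twice the upper expected value of 1.5. Even at those most adverse inputs (15 patients at 0.10 each), the chance of three or more is 1 − (0.206 + 0.343 + 0.267) = about 18%. The symmetry also means that a net distortion of the comparison requires worsening to be more common on drug.

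**Conclusion.** The point holds in a limited form. As written, the rule leaves a rise in grade after crossover out of the later treatment's column. For a placebo-first patient whose event worsens because of LJN452, the drug column is understated by 3.3 points (N = 30) or 4.2 points (24 completers).

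The number of such patients cannot be derived from the documents. Under the assumed ranges for p and s it is about 0.1 to 1.5, an expected understatement of 0.25 to 5.0 points. This rests on worsening being recorded within the existing event, as Protocol 9.1 suggests, and on the event lasting through at least 7 days of washout.

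The correction is worth making because the table serves a primary objective and a listing does not correct a percentage. It is not a reason to doubt the safety analysis as a whole.

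**What to change.** In SAP 7.1.2 and Protocol 11.5.2:

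- Also count an adverse event under the later period's treatment if its CTCAE grade increases, or it becomes serious, after that period's first dose.
- Leave events that continue unchanged in the onset period only.
- Keep the onset-only count as a secondary display.
- Footnote that a worsened event can appear in both columns.
- State which treatment takes an event that begins during washout, which the present rule leaves open.

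Add a CRF instruction to record the date of grade change. Protocol 9.1 requires changes in severity to be assessed but does not list that date among the items recorded, so the new count cannot be relied on without it. It needs to be captured prospectively.

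The cost is a short text change in two places, slightly more data capture, and one extra display. The drawback is that some natural fluctuation in grade will be counted under the later treatment, in either sequence.
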